- 10. Any condition which, in the opinion of the investigator, might jeopardize the safety of study participants or interfere with the evaluation of the study objectives.
- 11. Receipt of antimicrobial drugs for any reason within 14 days before vaccination.
- 12. History of diarrhea during the 7 days before vaccination (see protocol definition of diarrhea).
- 13. Culture positive for ETEC, Shigella, V.cholerae, Salmonella or Rotavirus (the latter for all children <5 years of age).

- 14. Acute disease at the time of enrollment or 3 days prior to enrollment.
- 15. Known or suspected impairment of immunological function based on medical history and physical examination.
- 16. Participant's parents/guardians not able, available or willing to accept active weekly follow-up by the study staff.
- 17. History of chronic administration (defined as more than 14 days) of immunosuppressant medications, including corticosteroids. Infants on inhaled or topical steroids may be permitted to participate in the study.
- 18. Any medical condition in the parents/infant that, in the judgement of the investigator, would interfere with or serves as a contraindication to protocol adherence or a participant's parents' ability to give informed consent.
- 19. Medically significant malnutrition, defined as moderate malnutrition (wt-for-ht z-score between -3.0 and -2.0) and severe malnutrition (wt-for-ht z-score <-3.0 or edema).

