9.6 Concomitant Medications

Concomitant medications are those medications taken at the same time or after vaccination. Prior medications are those medications that were started and stopped prior to vaccination. Both prior and concomitant medications will be classified according to a standardized drug code. The use of prior and concomitant medications taken during the study will be summarized by medication name and treatment group (Tables 14.3.6(a)(b)(c)(d)).

Individual participant listings will be presented for all prior and concurrent medications (Listings 16.2.10(a)(b)(c)(d)).

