Programming Note: Use same format as Figure 14.3.5.1a - except use treatment groups: ETVAX 3.5 mL, ETVAX 7mL, ETVAX ## + 2.5 µg dmLT, ETVAX ## + 5 µg dmLT, Placebo

FIGURE 14.3.5.1d:

Vital Sign Measurements by Scheduled Visits: Mean Changes from Baseline by Vital Sign and Treatment Group - Infants (6 - 11 Months)

Programming Note: Use same format as Figure 14.3.5.1a - except use treatment groups: ETVAX 1.75 mL, ETVAX 3.5 mL, ETVAX 7mL, ETVAX ## + 2.5 µg dmLT, ETVAX ## + 5 µg dmLT, Placebo

TABLE 14.3.6a: Number and Percentage of Participants with Prior and Concurrent Medications by Treatment Group - Adults

	Plac (N=		ETVAX Full Dose (N=X)		ETVAX Full Dose + 10 μg dmLT (N=X)		All Participants (N=X)	
Medication Name	n	%	n	%	n	%	n	%
Any Medication	X	x.x	X	X.X	Х	X.X	Х	x.x
[Medication 1]	X	x.x	X	X.X	Х	x.x	X	x.x
[Medication 2]	X	x.x	X	X.X	Х	X.X	Х	x.x
[Medication 3]	X	x.x	X	X.X	X	x.x	X	X.X

N = Number of participants in the Safety population. n = Number of participants reporting taking at least one medication in the medication class. A participant will only be counted once in each row.

TABLE 14.3.6b:

Number and Percentage of Participants with Prior and Concurrent Medications by Treatment Group - Toddlers (24 - 59 Months)

	Placebo (N=XX)			ETVAX 1/4 Dose (N=XX)		ETVAX 1/2 Dose (N=XX)		ETVAX Full Dose (N=XX)		Combined ETVAX Alone (N=XX)	
Medication Name	n	%	n	%	n	%	n	%	n	%	
Any Medication	X	X.X	X	X.X	X	X.X	X	X.X	X	X.X	
[Medication 1]	Х	X.X	X	X.X	X	X.X	X	X.X	Х	X.X	
[Medication 2]	Х	X.X	X	X.X	X	X.X	X	X.X	Х	X.X	
[Medication 3]	X	x.x	x	x.x	X	X.X	X	x.x	X	X.X	

N = Number of participants in the Safety population. n = Number of participants reporting taking at least one medication in the medication class. A participant will only be counted once in each row.

	ETV (highest sa +2.5 μg (N=)	afe dose) dmLT	(highest s +5 μg	ETVAX (highest safe dose) +5 µg dmLT (N=XX)		ETVAX (highest safe dose) +10 µg dmLT (N=XX)		Combined ETVAX + dmLT (N=XX)		All Participants (N=XX)	
Medication Name	n	%	n	%	n	%	n	%	n	%	
Any Medication	Х	X.X	X	X.X	X	X.X	X	X.X	X	X.X	
[Medication 1]	Х	X.X	X	X.X	X	X.X	X	X.X	X	X.X	
[Medication 2]	Х	X.X	X	X.X	X	X.X	X	X.X	X	X.X	
[Medication 3]	X	X.X	X	X.X	X	X.X	X	X.X	X	X.X	

N = Number of participants in the Safety population. n = Number of participants reporting taking at least one medication in the medication class. A participant will only be counted once in each row.

TABLE 14.3.6c:
Number and Percentage of Participants with Prior and Concurrent Medications

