LISTING 16.2.9.1c: Vital Signs - Young Children (12 - 23 Months)

Programming Note: Use the same format as Listing 16.2.9.1a shell.

LISTING 16.2.9.1d: Vital Signs - Infants (6 - 11 Months)

Programming Note: Use the same format as Listing 16.2.9.1a shell.

LISTING 16.2.9.2a: Physical Exam Findings - Adults

Participant ID	Treatment Group	Planned Time Point	Actual Study Day	Body System	Abnormal Finding	Reported as AE? (AE Number)

[Implementation Note: This listing includes all physical exam findings, scheduled and unscheduled. If a participant does not have any findings upon examination, they will not be included in this listing.

If reported as an AE, display "Yes" with the AE Number in parentheses, e.g., "Yes (7)".]

LISTING 16.2.9.2b: Physical Exam Findings - Toddlers (24 - 59 Months)

Programming Note: Use the same format as Listing 16.2.9.2a shell.

LISTING 16.2.9.2c:

Physical Exam Findings - Young Children (12 - 23 Months)

Programming Note: Use the same format as Listing 16.2.9.2a shell.

LISTING 16.2.9.2d:

Physical Exam Findings - Infants (6 - 11 Months)

Programming Note: Use the same format as Listing 16.2.9.2a shell.

LISTING 16.2.10a: Concomitant Medications - Adults

Participant ID	Treatment Group	CM Number	Medication	Medication Start Day	Medication End Day	Indication	Taken for an AE? (AE Number)	Taken for a condition on Medical History? (MH Number)

[Implementation Note: "Medication Start Day" and "Medication End Day" are relative to enrollment (which is Day 1, day before enrollment is Day -1). For medication start dates that are > 30 days prior to enrollment, rather than use exact study days, categorize as follows:

- >5 years prior to enrollment
- 1-5 years prior to enrollment
- 1-12 months prior to enrollment

If ongoing, display "Ongoing" in the "Medication End Day" column.

If taken for an AE or MH, display "Yes" with the AE or MH Number in parentheses, e.g., "Yes (7)".]

LISTING 16.2.10b: Concomitant Medications - Toddlers (24 - 59 Months)

Participant ID	Treatment Group	CM Number	Medication	Medication Start Day	Medication End Day	Indication	Taken for an AE? (AE Number)	Taken for a condition on Medical History? (MH Number)

[Implementation Note: "Medication Start Day" and "Medication End Day" are relative to enrollment (which is Day 1, day before enrollment is Day -1). For medication start dates that are > 30 days prior to enrollment, rather than use exact study days, categorize as follows:

- > 1 year prior to enrollment

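### Tables 14.3.6a-d pool medication use before and after vaccination, so no summary table shows post-vaccination medication use by arm

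*SAP*

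**What the plan says.** SAP Section 9.6 sets two definitions divided at vaccination: "Prior medications are those medications that were started and stopped prior to vaccination" and "Concomitant medications are those medications taken at the same time or after vaccination". Section 3.3, item 15, repeats the first as a derived variable. Section 9.6 then sends both to one set of tables: "The use of prior and concomitant medications taken during the study will be summarized by medication name and treatment group".

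The shells carry this out. Table 14.3.6a is titled "Number and Percentage of Participants with Prior and Concurrent Medications by Treatment Group - Adults", and Tables 14.3.6b-d have the same title for the three paediatric groups. The rows are one any-medication row followed by medication names, and the columns are treatment groups. Nothing marks timing relative to vaccination. The footnote adds "A participant will only be counted once in each row". It also defines n as "Number of participants reporting taking at least one medication in the medication class", although the rows and Section 9.6 both work by medication name.

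Medication start and end days, the indication and a link to an adverse event appear only in Listings 16.2.10a-d, participant by participant.

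**The concern.** Section 4.4.2 places randomisation on the day of the first vaccination, immediately before immunisation. Under the SAP's own definition, a prior medication is therefore baseline background that the vaccine cannot affect. When it is counted in the same row as treatment given after a dose, and each participant counts once, the two cannot be told apart and the arms look more alike than their post-vaccination use was.

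Elsewhere the SAP keeps the two periods apart. Pre-existing conditions have their own tables (Section 7.4, Tables 14.1.5a-d), and unsolicited events are tabulated by days after vaccination (Section 9.1.2). Only medication use is pooled.

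At stake is a descriptive summary that could support the primary safety and tolerability objective: how many participants in each arm took medication after vaccination. As designed, the table cannot answer that question.

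**Working it through.** The SAP states no rate, power or sample size for medication use, so there is no planned figure to reproduce. The check has a structural part and an arithmetic part.

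**Structure.** In all four shells the row label is the medication name, the column is the treatment group, and the count is one per participant per row. A participant with only prior use and one with only post-vaccination use both add 1 to the same cell. None of the planned summary tables reports concomitant use alone.

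**Inputs for the arithmetic.** None of these is in the SAP; all are assumptions.
- p0 and p1: post-vaccination use in the placebo and vaccine arms, taken as 10% and 30%, a 20-point difference.
- q: the fraction with prior use in that row, assumed equal in both arms and independent of later use. It is varied from 0 to 75%.

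**Formula.** A participant is absent from the row only if there was neither prior nor later use, so

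pooled rate P = 1 - (1-q)(1-p).

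Subtracting the arms gives P1 - P0 = (1-q)(p1 - p0).

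| q | Placebo, printed | Vaccine, printed | Printed difference |
|---|---|---|---|
| 0% | 10% | 30% | 20 points |
| 10% | 19% | 37% | 18 points |
| 25% | 32.5% | 47.5% | 15 points |
| 50% | 55% | 65% | 10 points |
| 75% | 77.5% | 82.5% | 5 points |

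For example, at q = 25% the placebo figure is 1 - 0.75 × 0.90 = 0.325 and the vaccine figure is 1 - 0.75 × 0.70 = 0.475.

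The factor (1-q) does not depend on the choice of p0 and p1. Dilution is absent in a row only when q = 0 there. The relevant q differs by row: the any-medication row takes prior use of any drug, while a named-drug row takes prior use of that drug alone. At q = 5% in a named-drug row, 20 points would print as 0.95 × 20 = 19.

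**The case against.** The strongest reply is that nothing in the plan turns on this table. The primary endpoints are SAEs, AEs and reactogenicity (Section 3.2.1). Each has its own post-vaccination reporting: solicited events compared by Fisher's exact test (Section 9.1.1), unsolicited events by severity, relationship and time since vaccination (Section 9.1.2), and SAEs listed (Section 9.2). Medication use is neither an endpoint nor tested. This stands, and it limits the weight of the point.

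Second, the data are not lost. Listings 16.2.10a-d give treatment group, start and end days and the AE link, and vaccine arms are planned at only 15 or 30 participants. This also stands, though a participant-level listing is not a summary by arm.

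Third, q may be small. Participants are healthy. One exclusion for adults, repeated for children, is "Receipt of antimicrobial drugs for any reason within 14 days before vaccination", and others cover recent iron or zinc and current antacids or immunosuppressive drugs. The Section 9.6 phrase about use during the study could confine prior use to the interval after a screening evaluation held at most 7 days before vaccination. The SAP does not settle that reading, and the definitions and all four titles still include prior use. The adult listing's instruction "For medication start dates that are > 30 days prior to enrollment, rather than use exact study days, categorize as follows" does not show that q is large: it concerns start dates, and a drug begun long ago but still taken at dose 1 is concomitant. The size therefore has to be shown from zero upwards.

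A reader might also infer that the pooling affects second-dose eligibility, because receipt of antimicrobials is a continued exclusion criterion (Section 4.3.2.3). It does not. That rule is applied to each participant before dose 2, and participants who do not receive both doses are reported in Tables 14.1.3a-d.

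**Conclusion.** The point holds as a minor defect in the table design. The SAP separates prior from concomitant medication and then pools them under an explicit counting rule, so no summary table shows post-vaccination use by arm. The printed difference is (1-q) times the post-vaccination one, assuming prior use is equal across arms and independent of later use. A 20-point difference would print as anything from 20 points (q = 0) to 5 points (q = 75%). The documents do not say where in that range the trial lies.

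A stronger reading, that the pooling could hide a safety signal or bias the primary safety conclusions, is not supported. Those conclusions rest on separate post-vaccination analyses, the medication table is descriptive, and the listings allow post-vaccination use to be reconstructed.

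The footnote's reference to medication class over rows labelled by name is a separate wording inconsistency. It needs no assumption about q and does not cause the dilution.

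**What to change.** Split each of Tables 14.3.6a-d into two blocks using the Section 9.6 definitions, anchored at the date of dose 1:

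- **Prior:** started and stopped before dose 1.
- **Concomitant:** taken on or after dose 1, in two sub-blocks, one for medications newly started on or after dose 1 and one for those continued from before.

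The sub-division matters because a single concomitant block would still count long-standing medication that was merely continued together with treatment begun after the vaccine. Give each block and sub-block its own any-medication row, with each participant counted once per row within it.

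Change the footnote so that n is defined by medication name, to agree with the row labels and Section 9.6.

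The cost is a revised shell and longer tables. The start and end days and vaccination dates needed are already planned for Listings 16.2.10a-d and 16.2.5a-d, so no new data are required.

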08 AUG 2018
Version 2.0

14.2 DATA LISTINGS

LISTING 16.2.1a: Early Terminations or Discontinued Participants - Adults

Participant ID	Treatment Group	Category	Reason for Early Termination	Study Day

LISTING 16.2.1b:

Early Terminations or Discontinued Participants - Toddlers (24 - 59 Months)

Programming Note: Use the same format as Listing 16.2.1a shell.

LISTING 16.2.1c:

Early Terminations or Discontinued Participants - Young Children (12 - 23 Months)

Programming Note: Use the same format as Listing 16.2.1a shell.

LISTING 16.2.1d:

Early Terminations or Discontinued Participants - Infants (6 - 11 Months)

Programming Note: Use the same format as Listing 16.2.1a shell.

PATH Protocol: VAC 014/OEV-122 ERC/PR-14127
Statistical Analysis Plan: Appendix II - Listings

08 AUG 2018
Version 2.0

LISTING 16.2.2.1a: Participant-Specific Protocol Deviations - Adults

Participant ID	Treatment Group	DV Number	Deviation	Deviation Category	Study Day	Reason for Deviation	Deviation Resulted in AE?	Deviation Resulted in Participant Termination?	Deviation Affected Product Stability?	Deviation Resolution	Comments

LISTING 16.2.2.1b:

Participant-Specific Protocol Deviations - Toddlers (24 - 59 Months)

Programming Note: Use the same format as Listing 16.2.2.1a shell.

LISTING 16.2.2.1c:

Participant-Specific Protocol Deviations - Young Children (12 - 23 Months)

Programming Note: Use the same format as Listing 16.2.2.1a shell.

LISTING 16.2.2.1d:

Participant-Specific Protocol Deviations - Infants (6 - 11 Months)

Programming Note: Use the same format as Listing 16.2.2.1a shell.

PATH Protocol: VAC 014/OEV-122 ERC/PR-14127
Statistical Analysis Plan: Appendix II - Listings

08 AUG 2018
Version 2.0

LISTING 16.2.2.2a: Non-Participant-Specific Protocol Deviations - Adults

Site	Deviation	Start Date	End Date	Reason for Deviation	Deviation Resulted in Participant Termination?	Deviation Affected Product Stability?	Deviation Category	Deviation Resolution	Comments

LISTING 16.2.2.2b:

Non-Participant-Specific Protocol Deviations - Toddlers (24 - 59 Months)

Programming Note: Use the same format as Listing 16.2.2.2a shell.

LISTING 16.2.2.2c:

Non-Participant-Specific Protocol Deviations - Young Children (12 - 23 Months)

Programming Note: Use the same format as Listing 16.2.2.2a shell.

LISTING 16.2.2.2d:

Non-Participant-Specific Protocol Deviations - Infants (6 - 11 Months)

Programming Note: Use the same format as Listing 16.2.2.2a shell.

LISTING 16.2.3a: Participants Excluded from the Immunogenicity Analysis - Adults

Treatment Group	Participant ID	Analyses in which Participant is Included	Analyses from which Participant is Excluded	Results Available?	Reason Participant Excluded
		[e.g., Safety, ITT, PP]	[e.g., Safety, ITT, PP, Day x]		

LISTING 16.2.3b:

Participants Excluded from the Immunogenicity Analysis - Toddlers (24 - 59 Months)

Programming Note: Use the same format as Listing 16.2.3a shell.

LISTING 16.2.3c:

Participants Excluded from the Immunogenicity Analysis - Young Children (12 - 23 Months)

Programming Note: Use the same format as Listing 16.2.3a shell.

LISTING 16.2.3d:

Participants Excluded from the Immunogenicity Analysis - Infants (6 - 11 Months)

Programming Note: Use the same format as Listing 16.2.3a shell.

LISTING 16.2.4.1a: Demographic Data - Adults

Participant ID	Treatment Group	Sex	Age at Enrollment (years)	Ethnicity	Race	Height at Enrollment (cm)	Weight at Enrollment (kg)

LISTING 16.2.4.1b: Demographic Data - Toddlers (24 - 59 Months)

Participant ID	Treatment Group	Sex	Age at Enrollment (months)	Ethnicity	Race	Length at Enrollment (cm)	Weight at Enrollment (kg)

LISTING 16.2.4.1c: Demographic Data - Young Children (12 - 23 Months)

Participant ID	Treatment Group	Sex	Age at Enrollment (months)	Ethnicity	Race	Length at Enrollment (cm)	Weight at Enrollment (kg)	Gestational Age at Delivery (weeks)	Birth Weight (kg)

LISTING 16.2.4.1d: Demographic Data - Infants (6 - 11 Months)

			Age at Enrollment			Length at Enrollment	Weight at Enrollment	Gestational Age at Delivery	Birth Weight
Participant ID	Treatment Group	Sex	(months)	Ethnicity	Race	(cm)	(kg)	(weeks)	(kg)

LISTING 16.2.4.2a: Pre-Existing Medical Conditions - Adults

Participant ID	Treatment Group	Medical History Term	Condition Start Day	Condition End Day	MedDRA® System Organ Class	MedDRA® Preferred Term

- > 5 years prior to enrollment
- 1-5 years prior to enrollment
- 1-12 months prior to enrollment
- Within 1 month of enrollment
- During study
- If ongoing, display "Ongoing" in the "Condition End Day" column]

LISTING 16.2.4.2b: Pre-Existing Medical Conditions - Toddlers (24 - 59 Months)

Participant ID	Treatment Group	MH Number	Medical History Term	Condition Start Day	Condition End Day	MedDRA® System Organ Class	MedDRA® Preferred Term

- > 1 year prior to enrollment
- 1-12 months prior to enrollment
- Within 1 month of enrollment
- During study
- If ongoing, display "Ongoing" in the "Condition End Day" column]

LISTING 16.2.4.2c: Pre-Existing Medical Conditions - Young Children (12 - 23 Months)

Participant ID	Treatment Group	MH Number	Medical History Term	Condition Start Day	Condition End Day	MedDRA® System Organ Class	MedDRA® Preferred Term

- > 6 months prior to enrollment
- 1-5 months prior to enrollment
- Within 1 month of enrollment
- During study
- If ongoing, display "Ongoing" in the "Condition End Day" column]

LISTING 16.2.4.2d: Pre-Existing Medical Conditions - Infants (6 - 11 Months)

Participant ID	MH Number	Medical History Term	Condition Start Day	Condition End Day	MedDRA® System Organ Class	MedDRA® Preferred Term

- > 1 month prior to enrollment
- Within 1 month of enrollment
- During study
- If ongoing, display "Ongoing" in the "Condition End Day" column]

LISTING 16.2.5a: Compliance Information/Vaccination Dates - Adults

		Vaccina	ation Dates	
Participant ID	Treatment Group	First	Second	Both doses the same ?
				Y/N

LISTING 16.2.5b: Compliance Information/Vaccination Dates - Toddlers (24 - 59 Months)

		Vaccin	ation Dates	
Participant ID	Treatment Group	First	Second	Both doses the same ?
				Y/N

LISTING 16.2.5c: Compliance Information/Vaccination Dates - Young Children (12 - 23 Months)

		Vaccina	ation Dates	
Participant ID	Treatment Group	First	Second	Both doses the same ?
				Y/N

LISTING 16.2.5d: Compliance Information/Vaccination Dates - Infants (6 - 11 Months)

		Vaccin	ation Dates	
Participant ID	Treatment Group	First	Second	Both doses the same ?
				Y/N

Statistical Analysis Plan: Appendix II - Listings

LISTING 16.2.6.1a: Individual Immunogenicity Response Data for Antibody Lymphocyte Secretion IgA - Adults

				Antigen					
Participant ID	Treatment Group	Planned Time Point	Actual Study Day	LTB	CFA/I	CS3	CS6	CS5	078 LPS

LISTING 16.2.6.1b:

Individual Immunogenicity Response Data for Antibody Lymphocyte Secretion IgA - Toddlers (24 - 59 Months)

Programming Note: Use the same format as Listing 16.2.6.1a shell.

LISTING 16.2.6.1c:

Individual Immunogenicity Response Data for Antibody Lymphocyte Secretion IgA - Young Children (12 - 23 Months)

Programming Note: Use the same format as Listing 16.2.6.1a shell.

LISTING 16.2.6.1d:

Individual Immunogenicity Response Data for Antibody Lymphocyte Secretion IgA - Infants (6 - 11 Months)

Programming Note: Use the same format as Listing 16.2.6.1a shell.

LISTING 16.2.6.2a: Individual Immunogenicity Response Data for Fecal Secretion IgA - Adults

				Antigen					
Participant ID	Treatment Group	Planned Time Point	Actual Study Day	LTB	CFA/I	CS3	CS6	CS5	078 LPS

LISTING 16.2.6.2b:

Individual Immunogenicity Response Data for Fecal Secretion IgA - Toddlers (24 - 59 Months)

Programming Note: Use the same format as Listing 16.2.6.2a shell.

LISTING 16.2.6.2c:

Individual Immunogenicity Response Data for Fecal Secretion IgA - Young Children (12 - 23 Months)

Programming Note: Use the same format as Listing 16.2.6.2a shell.

LISTING 16.2.6.2d:

Individual Immunogenicity Response Data for Fecal Secretion IgA - Infants (6 - 11 Months)

Programming Note: Use the same format as Listing 16.2.6.2a shell.

LISTING 16.2.6.3a: Individual Immunogenicity Response Data for Plasma ELISA - Adults

	Treatment Plan		Actual				IgG Antigen				
Participant ID	Group	Time Point		LTB	CFA/I	CS3	CS6	CS5	078 LPS	LTB	078 LPS

LISTING 16.2.6.3b:

Individual Immunogenicity Response Data for Plasma ELISA - Toddlers (24 - 59 Months)

Programming Note: Use the same format as Listing 16.2.6.2a shell.

LISTING 16.2.6.3c:

Individual Immunogenicity Response Data for Plasma ELISA - Young Children (12 - 23 Months)

Programming Note: Use the same format as Listing 16.2.6.2a shell.

LISTING 16.2.6.3d:

Individual Immunogenicity Response Data for Plasma ELISA - Infants (6 - 11 Months)

Programming Note: Use the same format as Listing 16.2.6.2a shell.

LISTING 16.2.6.4a: Individual Data for T cell and Other Immune Responses - Adults

					Antigen				
Participant ID	Treatment Group	Assay	Planned Time Point	Actual Study Day	LTB	CFA/I	CS3	CS6	CS5

LISTING 16.2.6.4b:

Individual Data for T cell and Other Immune Responses - Toddlers (24 - 59 Months)

Programming Note: Use the same format as Listing 16.2.6.4a shell.

LISTING 16.2.6.4c:

Individual Data for T cell and Other Immune Responses - Young Children (12 - 23 Months)

Programming Note: Use the same format as Listing 16.2.6.4a shell.

LISTING 16.2.6.4d:

Individual Data for T cell and Other Immune Responses - Infants (6 - 11 Months)

Programming Note: Use the same format as Listing 16.2.6.4a shell.

LISTING 16.2.7.1a: Solicited Events - Adults

Participant ID	Treatment Group	Vaccination	Post Dose Day	Assessment*	Oral Temperature	Nausea	Vomiting	Loose Stools	Diarrhea	Abdominal Pain/Stomach Ache	Acute Systemic Allergic Reaction
				MA							
				Clinic							

^{*} MA = Data reported by participant on the Memory Aid and reviewed by clinic staff and reported in Solicited Events eCRF.

Clinic = Data collected by clinic staff during physical exam or symptom assessment (treatment administration record, in-clinic assessment, etc.)

[Implementation Note: To indicate severity for quantitative symptoms (e.g., temperature) measurements, include the grade in parentheses after the number, e.g., 100.7 (Mild).]

LISTING 16.2.7.1b: Solicited Events - Toddlers (24 - 59 Months)

Participant	Treatment ID Group	Vaccination	Post Dose Day	Assessment*	Oral Temperature	Vomiting	Loose Stools	Diarrhea	Abdominal Pain/Stomach Ache	Acute Systemic Allergic Reaction
				MA						
				Clinic						

^{*} MA = Data reported by participant on the Memory Aid and reviewed by clinic staff and reported in Solicited Events eCRF.

Clinic = Data collected by clinic staff during physical exam or symptom assessment (treatment administration record, in-clinic assessment, etc.)

[Implementation Note: To indicate severity for quantitative symptoms (e.g., temperature) measurements, include the grade in parentheses after the number, e.g., 100.7 (Mild).]

LISTING 16.2.7.1c: Solicited Events - Young Children (12 - 23 Months)

Participant ID	Treatment Group	Vaccination	Post Dose Day	Assessment*	Oral Temperature	Vomiting	Loose Stools	Diarrhea	Acute Systemic Allergic Reaction
				MA					
				Clinic					

^{*} MA = Data reported by participant on the Memory Aid and reviewed by clinic staff and reported in Solicited Events eCRF.

Clinic = Data collected by clinic staff during physical exam or symptom assessment (treatment administration record, in-clinic assessment, etc.)

[Implementation Note: To indicate severity for quantitative symptoms (e.g., temperature) measurements, include the grade in parentheses after the number, e.g., 100.7 (Mild).]

LISTING 16.2.7.1d: Solicited Events - Infants (6 - 11 Months)

Participant ID	Treatment Group	Vaccination	Post Dose Day	Assessment*	Oral Temperature	Vomiting	Loose Stools	Diarrhea	Acute Systemic Allergic Reaction
				MA					
				Clinic					

^{*} MA = Data reported by participant on the Memory Aid and reviewed by clinic staff and reported in Solicited Events eCRF.

Clinic = Data collected by clinic staff during physical exam or symptom assessment (treatment administration record, in-clinic assessment, etc.)

[Implementation Note: To indicate severity for quantitative symptoms (e.g., temperature) measurements, include the grade in parentheses after the number, e.g., 100.7 (Mild).]

LISTING 16.2.7.2a: Unsolicited Adverse Events - Adults

Participant ID	Treatment Group	AE Number	Adverse Event	# of Days Post Dose (Dose #)	Duration (Days)	Severity	SAE?	Relationship to Study Treatment	If Not Related, Alternate Etiology	Action Taken with Study Treatment

Participant ID	Adverse Event	Action Taken with Study Treatment	Participant Discontinued Due to AE	Outcome	MedDRA® System Organ Class	MedDRA® Preferred Term	Comments

Note: For additional details about SAEs, see Table: 14.3.2.1.

LISTING 16.2.7.2b: Unsolicited Adverse Events - Toddlers (24 - 59 Months)

Programming Note: Use the same format as Listing 16.2.7.2a shell.

LISTING 16.2.7.2c: Unsolicited Adverse Events - Young Children (12 - 23 Months)

Programming Note: Use the same format as Listing 16.2.7.2a shell.

LISTING 16.2.7.2d: Unsolicited Adverse Events - Infants (6 - 11 Months)

Programming Note: Use the same format as Listing 16.2.7.2a shell.

LISTING 16.2.8.1a: Individual Clinical Laboratory Results – Hematology - Adults

Participant ID	Treatment Group	Sex	Age (years)	Planned Study Day	Actual Study Day	Hemoglobin (g/dL)	Platelets (10 ⁹ /L)	White Blood Cells (10 ⁹ /L)	Neutrophils (10 ⁹ /L)	Lymphocytes (10 ⁹ /L)

[Implementation Note: This listing includes all laboratory results, scheduled and unscheduled. The severity should be included in parentheses after the result of the abnormal results (e.g., 16.2 (Mild)).]

LISTING 16.2.8.1b:

Individual Clinical Laboratory Results – Hematology - Toddlers (24 - 59 Months)

Programming Note: Use the same format as Listing 16.2.8.1a shell.

LISTING 16.2.8.1c:

Individual Clinical Laboratory Results – Hematology - Young Children (12 - 23 Months)

Programming Note: Use the same format as Listing 16.2.8.1a shell.

LISTING 16.2.8.1d:

Individual Clinical Laboratory Results – Hematology - Infants (6 - 11 Months)

Programming Note: Use the same format as Listing 16.2.8.1a shell.

LISTING 16.2.8.2a: Individual Clinical Laboratory Results – Biochemistry - Adults

Participant ID	Treatment Group	Sex	Age	Planned Study Day	Actual Study Day	ALT (IU/L)	Serum Creatinine (mg/dL)	Albumin (g/dL)	Total Bilirubin (mg/dL)

[Implementation Note: This listing includes all laboratory results, scheduled and unscheduled. The severity should be included in parentheses after the result of the abnormal results (e.g., 16.2 (Mild)).]

LISTING 16.2.8.2b:

Individual Clinical Laboratory Results – Biochemistry - Toddlers (24 - 59 Months)

Programming Note: Use the same format as Listing 16.2.8.2a shell.

LISTING 16.2.8.2c:

Individual Clinical Laboratory Results – Biochemistry - Young Children (12 - 23 Months)

Programming Note: Use the same format as Listing 16.2.8.2a shell.

LISTING 16.2.8.2d:

Individual Clinical Laboratory Results – Biochemistry - Infants (6 - 11 Months)

Programming Note: Use the same format as Listing 16.2.8.2a shell.

LISTING 16.2.8.3a: Individual Clinical Laboratory Results – Serology - Adults

Participant ID	Treatment Group	Sex	Age (years)	Planned Study Day	Actual Study Day	HBsAg	Anti-HCV

[Implementation Note: This listing includes all laboratory results, scheduled and unscheduled.]

LISTING 16.2.8.3b:

Individual Clinical Laboratory Results – Serology - Toddlers (24 - 59 Months)

Programming Note: Use the same format as Listing 16.2.8.3a shell.

LISTING 16.2.8.3c:

Individual Clinical Laboratory Results – Serology - Young Children (12 - 23 Months)

Programming Note: Use the same format as Listing 16.2.8.3a shell.

LISTING 16.2.8.3d:

Individual Clinical Laboratory Results – Serology - Infants (6 - 11 Months)

Programming Note: Use the same format as Listing 16.2.8.3a shell.

LISTING 16.2.9.1a: Vital Signs - Adults

Participant ID	Treatment Group	Planned Study Day	Actual Study Day	Temperature (°Celsius)	Heart Rate (beats/min)	Respiratory Rate (breaths/min)

[Implementation Note: This listing includes all vital sign assessments, scheduled and unscheduled.]

LISTING 16.2.9.1b: Vital Signs - Toddlers (24 - 59 Months)

Programming Note: Use the same format as Listing 16.2.9.1a shell.

LISTING 16.2.9.1c: Vital Signs - Young Children (12 - 23 Months)

Programming Note: Use the same format as Listing 16.2.9.1a shell.

LISTING 16.2.9.1d: Vital Signs - Infants (6 - 11 Months)

Programming Note: Use the same format as Listing 16.2.9.1a shell.

LISTING 16.2.9.2a: Physical Exam Findings - Adults

Participant ID	Treatment Group	Planned Time Point	Actual Study Day	Body System	Abnormal Finding	Reported as AE? (AE Number)

[Implementation Note: This listing includes all physical exam findings, scheduled and unscheduled. If a participant does not have any findings upon examination, they will not be included in this listing.

If reported as an AE, display "Yes" with the AE Number in parentheses, e.g., "Yes (7)".]

LISTING 16.2.9.2b: Physical Exam Findings - Toddlers (24 - 59 Months)

Programming Note: Use the same format as Listing 16.2.9.2a shell.

LISTING 16.2.9.2c:

Physical Exam Findings - Young Children (12 - 23 Months)

Programming Note: Use the same format as Listing 16.2.9.2a shell.

LISTING 16.2.9.2d:

Physical Exam Findings - Infants (6 - 11 Months)

Programming Note: Use the same format as Listing 16.2.9.2a shell.

LISTING 16.2.10a: Concomitant Medications - Adults

Participant ID	Treatment Group	CM Number	Medication	Medication Start Day	Medication End Day	Indication	Taken for an AE? (AE Number)	Taken for a condition on Medical History? (MH Number)

[Implementation Note: "Medication Start Day" and "Medication End Day" are relative to enrollment (which is Day 1, day before enrollment is Day -1). For medication start dates that are > 30 days prior to enrollment, rather than use exact study days, categorize as follows:

- >5 years prior to enrollment
- 1-5 years prior to enrollment
- 1-12 months prior to enrollment

If ongoing, display "Ongoing" in the "Medication End Day" column.

If taken for an AE or MH, display "Yes" with the AE or MH Number in parentheses, e.g., "Yes (7)".]

LISTING 16.2.10b: Concomitant Medications - Toddlers (24 - 59 Months)

Participant ID	Treatment Group	CM Number	Medication	Medication Start Day	Medication End Day	Indication	Taken for an AE? (AE Number)	Taken for a condition on Medical History? (MH Number)

[Implementation Note: "Medication Start Day" and "Medication End Day" are relative to enrollment (which is Day 1, day before enrollment is Day -1). For medication start dates that are > 30 days prior to enrollment, rather than use exact study days, categorize as follows:

- > 1 year prior to enrollment
- 1-12 months prior to enrollment

If ongoing, display "Ongoing" in the "Medication End Day" column.

If taken for an AE or MH, display "Yes" with the AE or MH Number in parentheses, e.g., "Yes (7)".]

LISTING 16.2.10c: Concomitant Medications - Young Children (12 - 23 Months)

Participant ID	Treatment Group	CM Number	Medication	Medication Start Day	Medication End Day	Indication	Taken for an AE? (AE Number)	Taken for a condition on Medical History? (MH Number)

[Implementation Note: "Medication Start Day" and "Medication End Day" are relative to enrollment (which is Day 1, day before enrollment is Day -1). For medication start dates that are > 30 days prior to enrollment, rather than use exact study days, categorize as follows:

- > 6 months prior to enrollment
- 1-5 months prior to enrollment

If ongoing, display "Ongoing" in the "Medication End Day" column.

If taken for an AE or MH, display "Yes" with the AE or MH Number in parentheses, e.g., "Yes (7)".]

LISTING 16.2.10d: Concomitant Medications - Infants (6 - 11 Months)

Participant ID	Treatment Group	CM Number	Medication	Medication Start Day	Medication End Day	Indication	Taken for an AE? (AE Number)	Taken for a condition on Medical History? (MH Number)

[Implementation Note: "Medication Start Day" and "Medication End Day" are relative to enrollment (which is Day 1, day before enrollment is Day -1). For medication start dates that are > 30 days prior to enrollment, rather than use exact study days, categorize as follows:

• > 1 month prior to enrollment

If ongoing, display "Ongoing" in the "Medication End Day" column.

If taken for an AE or MH, display "Yes" with the AE or MH Number in parentheses, e.g., "Yes (7)".]

PATH Protocol: VAC 014/OEV-122 ERC/PR-14127
Statistical Analysis Plan: Appendix II - Listings

